SAE	Serious Adverse Event
SAP	Statistical Analysis Plan
SAS	Safety Analysis Set
SoA	Schedule of Assessments
SmPC	Summary of Product Characteristics
SS	Screened Set

Abbreviation	Definition
SUSAR	Suspected Unexpected Serious Adverse Reaction
TEAE	Treatment Emergent Adverse Event
TOMS	Technical Operational Measures
UV-A	Ultraviolet A
UV-B	Ultraviolet B
UTI	Urinary Tract Infection
VAS	Visual Analogue Scale
VASSI	Vulvar lichen sclerosus Area and Sign Severity Index
VLS	Vulvar Lichen Sclerosus (Note: in the context of this trial 'Vulvar' region includes the clitoris and periclitoral skin, interlabial sulci, labia minora, posterior fourchette and perineum, anal and perianal skin)
VQLI	Vulvar disease Quality of Life Index
w/w	Weight by weight
WI	Worst Itch
WI-NRS	Worst Itch – Numeric Rating Score
WPP	Worst Penetrative sex related Pain
WPP-NRS	Worst Penetrative sex related Pain – Numeric Rating Score
WP	Worst Pain
WP-NRS	Worst Pain – Numeric Rating Score

1 Protocol summary

1.1 Synopsis

Title	A parallel group (2-arm), randomised, double-blind, 12-week trial to explore the efficacy and safety of MC2-25 cream and MC2-25 vehicle in women diagnosed with vulvar lichen sclerosus (VLS).
Protocol Number (EU trial number)	MC2-25-C3 (EU-CT 2023-503516-32-00)
Rationale	VLS is a serious condition with major impact on the quality of life of affected women. There is evidence that urea-derived isocyanate could be an important triggering factor in the development of signs and symptoms in patients with VLS. There is a high unmet need for an authorised, efficient, and safe treatment of VLS. Topically applied cream with Ala-Gln as an effective isocyanate scavenger in form of MC2-25 cream may prove to be an effective and safe treatment of VLS.
Phase	Phase 2
Objectives	
Primary objective: To explore the efficacy of MC2-25 cream compared to MC2-25 vehicle in vulvar lichen sclerosus (VLS).
 
Secondary objectives:
 
• To explore the safety of MC2-25 cream compared to MC2-25 vehicle in VLS.• To explore the burden of VLS on women's lives.
Design	Multicentre, phase 2, randomised, double-blind, 2-arm, parallel-group, vehicle-controlled trial in VLS. The trial consists of 3 consecutive periods adding up to a maximum trial duration for each patient of 18 weeks: Screening (up to 4 weeks), Treatment (12 weeks) and Follow-Up (2 weeks).
Planned Sample Size:	33 patients will be randomised in a 1:1 ratio to MC2-25 cream or MC2-25 vehicle.
Trial population	
Main inclusion criteria:
 
• Women, of any race or ethnicity, who are ≥ 18 years of age at the time of screening.• Clinical diagnosis of VLS (i.e., biopsy for histological confirmation not required except if needed to rule out malignancy or differential diagnosis of e.g., vulvar lichen planus) made by either a dermatologist or a gynaecologist familiar with VLS.

- Presence of at least one of the following signs of VLS: a. Hyperkeratosis (i.e., patches/plaques of bright white skin with a ‘powdery’ texture) and/or b. Sclerosis (i.e., areas of yellowish/ivory white skin with a smooth/waxy/firm texture. Sclerosis is often seen at the tips of the labia minora, or on periclitoral or perineal skin) in at least one of the following vulvar areas: Clitoris and/or periclitoral skin (C); Right interlabial sulcus and labium minus (R); Left interlabial sulcus and labium minus (L); Posterior Fourchette and/or perineum (P) (see protocol section 8.5.1.2).
- First symptoms of VLS (e.g., itching and/or pain) noticed by the patient at least 6 months before baseline.
- At least moderate itch defined as average WI-NRS ≥ 4 at the Baseline visit (average WI-NRS is calculated as the average of all available and at least four WI-NRS scores which are to be reported once daily by the patient in the diary for 7 days prior to the Baseline visit (7 days in total)).

Main exclusion criteria:

- Any (other than VLS) ongoing localised or systemic disease involving the vulvar region – e.g., lichen planus, psoriasis, eczema, ulcerative colitis or known active infection (bacterial, viral or fungal).
- Ongoing or prior diagnosis of any genitoanal malignancy or pre-malignancy (e.g., differentiated intraepithelial neoplasia or squamous cell carcinoma).
- Any kind of ongoing cancer (or anti-cancer treatment within 3 months or 5 half-lives (whichever is longest) prior to the Baseline visit). Note: non-metastasising basal cell carcinoma which does not involve the genitoanal area is acceptable.
- Use of emollients (including but not limited to creams, ointments, oils, or soaps with emollient properties) on the vulvar region within 3 days prior to the Baseline visit. Note: Only water and, if necessary, a soap bar without emollient properties, may be used to wash the vulvar region (intimate hygiene) when bathing or showering from within 3 days prior to the Baseline visit.
- Use of any topical treatment on the vulvar region, including but not limited to calcineurin inhibitors, corticosteroids or anti-infectives within 14 days prior to the Baseline visit.
- Use of any light therapy on the vulvar region, including but not limited to UV-B, UV-A, and laser, within 28 days prior to the Baseline visit.

Main endpoints

[figure not shown]
Primary endpoint:

Mean change in weekly mean Worst Itch Numeric Rating Score (WI-NRS) recorded in the patient’s diary from Baseline to Week 12 for MC2-25 cream compared to MC2-25 vehicle. (Weekly mean WI-NRS is calculated as the average of WI-NRS values recorded in the patient’s diary for 7 days prior to the in-clinic visits).

Secondary endpoints:	
• Mean change in weekly mean Worst Pain Numeric Rating Score (WP-NRS) recorded in the patient's diary from Baseline to Week 12 for MC2-25 cream compared to MC2-25 vehicle. (Weekly mean WP-NRS is calculated as the average of WP-NRS values recorded in the patient's diary for 7 days prior to the in-clinic visits.)• Percentage of patients obtaining a ≥ 4-point improvement in weekly mean WI-NRS recorded in the patient's diary from Baseline to Week 12 for MC2-25 cream compared to MC2-25 vehicle.• Percentage of patients obtaining a ≥ 4-point improvement in weekly mean WP-NRS recorded in the patient's diary from Baseline to Week 12 for MC2-25 cream compared to MC2-25 vehicle.• Percentage of patients obtaining a ≥ 3-point improvement in weekly mean WI-NRS recorded in the patient's diary from Baseline to Week 12 for MC2-25 cream compared to MC2-25 vehicle.• Percentage of patients obtaining a ≥ 3-point improvement in weekly mean WP-NRS recorded in the patient's diary from Baseline to Week 12 for MC2-25 cream compared to MC2-25 vehicle.• Change in Skindex-29 domains from baseline to week 12 for MC2-25 cream compared to MC2-25 vehicle.
Other endpoints:	
• Frequencies of treatment emergent adverse events (AEs), SAEs, adverse drug reactions, AEs leading to treatment discontinuation or trial withdrawal, Other important AEs and deaths during the trial for MC2-25 cream compared to MC2-25 vehicle.• Mean changes in Vital signs from Baseline to week 12 for MC2-25 cream compared to MC2-25 vehicle.
Trial sites	6 sites will be opened in Denmark.
Investigational Medicinal Product	
Trial participants will be randomized (1:1) to receive either:
 
• MC2-25 cream (with active product ingredient) or• MC2-25 vehicle (without active product ingredient) 
The IMP must be applied after each toilet visit during the 12-week treatment period.

Participant duration (including follow-up)	For each participant, there will be three consecutive trial periods, adding up to a maximum trial duration of 18 weeks: 
• Screening (up to 4 weeks)• Treatment (12 weeks) and• Follow-up (2 weeks).
Statistical Methods	The primary endpoint, mean change in weekly mean Worst Itch – Numeric Rating Score (WI-NRS) from baseline to Week 12 for MC2-25 cream compared to MC2-25 vehicle, will be analysed by a mixed model of repeated measures (MMRM) adjusting for visit, menopausal status at baseline, urinary incontinence status (ICIQ-UI-SF score) at baseline and weekly mean WI-NRS

	at baseline. At Week 12, the estimated treatment difference will be reported together with the associated standard error, 95% confidence intervals and p-values based on F-statistics.
Benefit-risk	There are only few known potential risks associated with the investigational medicinal product or the trial, i.e., application site reaction, use during pregnancy or lack of effect due to use of MC2-25 vehicle. Use of a vehicle control is considered justified as there are no approved treatments for VLS in Europe, off label systemic treatments for VLS may be continued during the trial and the IMP is an emollient and emollients are normally recommended for VLS. In view of the major impact of VLS on patient's quality of life, the potential benefits of MC2-25 cream on VLS, and the benign safety profile of MC2-25 cream, the benefit-risk ratio for the current trial is considered positive.

1.2 Schematic of trial design

* Site to call patient on day (-11 to) -8 to remind about daily WI-NRS and WP-NRS assessment in diary (day-7 to day -1),

1.3 Schedule of assessments (SoA)

Table 1: Schedule of assessments

Trial Period	Screening		Treatment									FU
Visit Number ¹ (Visit name)	1 (Screening1)	2 (Screening 2)	3 (Baseline)	4	5	6	7	8	9	10 (EoT ²)	11 (FU ³)	
Trial Week			0	1	3	4	7	8	11	12	14	
Days from Baseline Visit Window	-28 to -8 NA	(-11 to) -8	0 NA	7 ±1	18 ±2	28 ±4	46 ±2	56 ±4	74 ±2	84 ±4	98 ±4	
Visit type ⁴	In-Clinic	Phone	In-Clinic	In-Clinic	Phone	In-Clinic	Phone	In-Clinic	Phone	In-Clinic	In-Clinic/ Phone	
Informed Consent ⁵	X											
Demographics	X											
Eligibility Assessment	X		X									
Medical History	X											
Menopausal status and Menstrual cycle status			X							X		
Prior & concomitant therapies ⁶	X		X	X	X	X	X	X	X	X	X	
VLS History	X											
VLS Patient Journey ⁷	X											
ICIQ-UI-SF			X							X		
WI-NRS and WP- NRS – in-clinic assessment ^{7,8}	X		X	X		X		X		X		

Trial Period	Screening		Treatment									FU
Visit Number ¹ (Visit name)	1 (Screening1)	2 (Screening 2)	3 (Baseline)	4	5	6	7	8	9	10 (EoT ²)	11 (FU ³)	
Trial Week			0	1	3	4	7	8	11	12	14	
Days from Baseline Visit Window	-28 to -8 NA	(-11 to) -8	0 NA	7 ± 1	18 ± 2	28 ± 4	46 ± 2	56 ± 4	74 ± 2	84 ± 4	98 ± 4	
Visit type ⁴	In-Clinic	Phone	In-Clinic	In-Clinic	Phone	In-Clinic	Phone	In-Clinic	Phone	In-Clinic	In-Clinic/ Phone	
WI-NRS and WP- NRS Diary (Handout) ⁹	X		X	X		X		X				
WI-NRS and WP- NRS diary completion reminder ⁴		X	X		X		X		X			
WI-NRS and WP- NRS Diary (return & review) ¹⁰			X	X		X		X		X		
WPP-NRS – in-clinic assessment ⁸	X		X			X		X		X		
Patient's Global Impression of Change (PGIC) ⁷						X		X		X		
Patient's rating of importance of improvement ⁷						X		X		X		
VQLI ⁷			X			X		X		X		
Skindex-29 ⁷			X			X		X		X		
Imaging of VLS ¹¹	X		X	X		X		X		X		
VASSI	X		X	X		X		X		X		
CGA	X		X	X		X		X		X		

Trial Period	Screening		Treatment									FU
Visit Number ¹ (Visit name)	1 (Screening1)	2 (Screening 2)	3 (Baseline)	4	5	6	7	8	9	10 (EoT ²)	11 (FU ³)	
Trial Week			0	1	3	4	7	8	11	12	14	
Days from Baseline Visit Window	-28 to -8 NA	(-11 to) -8	0 NA	7 ±1	18 ±2	28 ±4	46 ±2	56 ±4	74 ±2	84 ±4	98 ±4	
Visit type ⁴	In-Clinic	Phone	In-Clinic	In-Clinic	Phone	In-Clinic	Phone	In-Clinic	Phone	In-Clinic	In-Clinic/ Phone	
CGIC				X		X		X		X		
Physical examination ¹²	X		X							X	(X)	
Vital signs ¹³			X							X	(X)	
Urine pregnancy test ¹⁴	X		X	X		X		X		X	(X)	
Randomisation			X									
Application Diary (Handout)			X	X		X		X				
Application Diary (Return and review) ¹⁰				X		X		X		X		
Adverse events	X	X	X	X	X	X	X	X	X	X	X	
IMP dispensation			X			X		X				
IMP return, compliance and accountability						X		X		X		
IMP application ¹⁵							X					

1. An unscheduled visit can be conducted to perform any of the post-baseline assessments or procedures included in the schedule of assessments (SoA) if deemed necessary by the Investigator.
2. In the case of trial withdrawal or treatment discontinuation, all assessments of the Week 12 (End of Treatment [EoT]) visit must be performed to the extent possible. The end of treatment (EoT) form must be completed when treatment is permanently discontinued, and the end of trial form must be completed at end of the trial or in case of trial withdrawal.

3. (X) indicates assessments to be performed if judged necessary by the investigator. This visit could be an in-clinic visit or a phone visit depending on the follow up assessments considered needed by the investigator.
4. The patients should be reminded about when to fill in the WI-NRS and WP-NRS diary. In case of phone visits, the phone call should be made as close as possible to the first WI-NRS and WP-NRS diary completion day. **Note: if Screening 1 visit is performed on day -8, then Screening 2 visit will be omitted.**
5. Informed consent must be signed by both patient and investigator before any trial-related procedures are performed.
6. "Therapies" encompassing medications and non-pharmacological treatments.
7. At all in-clinic visits, all patient-reported outcome (PRO) assessments should be completed before all other clinical assessments or procedures.
8. The WI-NRS and WP-NRS must also be reported by the patient at in-clinic visits.
9. WI-NRS and WP-NRS diary assessments must be performed at home once daily (i.e., every day around the same timepoint, e.g., morning, afternoon, or evening) for a total of 7 days before each in-clinic visit (i.e., from day -7 to day -1 before the next in-clinic visit).
10. When returned the Diaries should be checked for completeness and any irregularities while the patient is still in the clinic.
11. Imaging is mandatory, and must be done at Screening 1, Baseline, Week 1, Week 4, Week 8 and Week 12 (or early termination).
12. Physical exam: A complete physical examination is required at Screening 1 and Week 12 (EoT or Early Termination) visits. An abbreviated physical examination is required at the Baseline visit and at the FU visit (if physical examination is judged necessary by the investigator).
13. Vital signs include blood pressure, heart rate, and body temperature measurement. Blood pressure and pulse rate must be taken with the patient in the sitting position with approximately 5 minutes rest prior to measurement.
14. Highly sensitive urine pregnancy tests are conducted for women of childbearing potential.
15. Before the first IMP application, the site staff shall provide thorough instruction to the patient regarding the area to apply the cream to, the amount of cream to be applied and the required frequency of application.

2 Introduction

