6.1.2 Dosing and administration

MC2-25 cream, or MC2-25 vehicle must be applied after each toilet visit following urination (during day and night) starting on the day of the Baseline visit. The MC2-25 cream, or MC2-25 vehicle should be applied by the patient in a thin saturating layer to the vulvar region (i.e., vulvar region includes clitoris and periclitoral skin, interlabial sulci, labia minora, posterior fourchette and perineum, anal and perianal skin). Approximately one fingertip-unit (FTU), roughly corresponding to 0.5 g cream is to be used after each toilet visit (during night and day). The vulvar region may be gently cleaned with water and dabbed dry with toilet paper or a clean cloth before each application of the trial treatment. Assuming, a maximum of 12 toilet visits are needed over a period of 24 hours, the maximum daily dose is expected to be around 6.0 g. A treatment application manual will be available for patients.

Reference is made to Section 4.2 for the rationale behind the dosing-regimen.

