8.5.2 Patient reported outcomes (PRO) assessments

8.5.2.1 Worst Itch Numeric Rating Score (WI-NRS) of VLS

The patient's WI-NRS score must be recorded by the patient in a diary once daily (i.e., every day around the same timepoint, e.g. morning, afternoon or evening) for a total of 7 days (i.e. starting 7 days before the next in-clinic visit and ending on the day before the next in-clinic visit) leading up to each in-clinic visit day at Baseline, Week 1, Week 4, Week 8, and Week 12 (or Early Termination) using an 11-point numeric rating scale ranging from 0 to 10:

Please score the intensity of the Worst Itch associated with your lichen sclerosus, that you have experienced in the past 24 hours: 0 (no itch), 1, 2, 3, 4, 5, 6, 7, 8, 9, 10 (worst imaginable itch).

In addition, the patient's WI-NRS score must be reported to the clinical staff at in-clinic visits at Screening 1, Baseline, Week 1, Week 4, Week 8, and Week 12 or Early Termination using the 11-point numeric rating scale above.

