## 2.4 Study Endpoints

### 2.4.1 Efficacy

The primary endpoint is the mean change in weekly mean Worst Itch Numeric Rating Score (WI-NRS) recorded in the patient's diary from Baseline to Week 12 for *MC2-25 cream* compared to *MC2-25 vehicle*.

(Weekly mean WI-NRS is calculated as the average of WI-NRS values recorded in the patient's diary for 7 days prior to the in-clinic visits).

The secondary endpoints (all defined from Baseline to Week 12 for MC2-25 cream compared to MC2-25 vehicle) are:

- Mean change in weekly mean Worst Pain Numeric Rating Score (WP-NRS) recorded in the patient's diary (Weekly mean WP-NRS is calculated as the average of WP-NRS values recorded in the patient's diary for 7 days prior to the in-clinic visits.)
- Percentage of patients obtaining a  $\geq 4$ -point improvement in weekly mean WI-NRS recorded in the patient's diary
- Percentage of patients obtaining a  $\geq 4$ -point improvement in weekly mean WP-NRS recorded in the patient's diary
- Percentage of patients obtaining a  $\geq 3$ -point improvement in weekly mean WI-NRS recorded in the patient's diary
- Percentage of patients obtaining a  $\geq 3$ -point improvement in weekly mean WP-NRS recorded in the patient's diary
- Change in Skindex-29 domains

Primary and secondary endpoints will be confirmatorily analyzed as described in Sections 5.2 to 5.5. Other endpoints will be exploratorily analyzed.

Other endpoints (all defined from Baseline to Week 12) include:

- Percentage of patients obtaining a complete response (score  $\leq 1$ ) in weekly mean WI-NRS recorded in the patient's diary
- Percentage of patients obtaining a complete response (score  $\leq 1$ ) in weekly mean WP-NRS recorded in the patient's diary
- Mean change in Worst Itch Numeric Rating Score (WI-NRS) recorded at in-clinic visits
- Mean change in Worst Pain Numeric Rating Score (WP-NRS) recorded at in-clinic visits
- Mean change in Worst Penetrative sex related Pain Numeric Rating Score (WPP-NRS) recorded at in-clinic visits
- Percentage of patients obtaining a  $\geq 3$ -point improvement in WI-NRS recorded at in-clinic visits
- Percentage of patients obtaining a  $\geq 3$ -point improvement in WP-NRS recorded at in-clinic visits
- Percentage of patients obtaining a  $\geq 3$ -point improvement in WPP-NRS recorded at in-clinic visits

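### The Week 1 weekly itch and pain means can include the diary entry from the day treatment starts and, after a Day 6 visit, possibly one from the day before; Week 12 is almost unaffected

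*Protocol*

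**What the plan says.** - **Diary window.** Protocol 1.3, footnote 9, asks for one home entry a day "for a total of 7 days before each in-clinic visit (i.e., from day -7 to day -1 before the next in-clinic visit".
- **Derivation.** SAP 2.4.1: "Weekly mean WI-NRS is calculated as the average of WI-NRS values recorded in the patient's diary for 7 days prior to the in-clinic visits". The pain score is derived in the same way. Neither document says what to do with entries dated on or before the first application.
- **Recall.** Protocol 8.5.2.1 asks for the worst itch "that you have experienced in the past 24 hours", scored "every day around the same timepoint, e.g. morning, afternoon or evening". Section 8.5.2.2 does the same for pain.
- **Start of treatment.** Protocol 6.1.2 has the cream applied "starting on the day of the Baseline visit", which is Day 0.
- **Week 1 visit.** The schedule in Protocol 1.3 puts it on Day 7 ±1, counted from Baseline.
- **Separate diaries.** In the same schedule the row "WI-NRS and WP- NRS Diary (Handout" is marked at Screening 1, Baseline and Weeks 1, 4 and 8. The screening diary is returned at Baseline, so the Week 1 diary exists only from Day 0.
- **Visit windows.** SAP 4.6.2 selects visits, not diary days.

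**The concern.** A value labelled post-baseline should describe the patient on treatment. Under the stated rule, the first such value can average in scores that are wholly or mostly untreated, and the number depends on which permitted day the patient attends. Because the item asks for the worst score in 24 hours, a few untreated hours can set the whole entry.

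Week 1 is the earliest post-baseline efficacy time point. It receives within-arm t-tests (SAP 3.2.2), within-arm exact tests of improvement rates (SAP 3.2.1), box plots and responder bar charts (SAP 7.4), and an exploratory treatment difference (SAP 5.2). It is also one of the repeated measures in the primary model (Protocol 9.4.2.1) and the first step of the multiple imputation (SAP 4.7.2). At stake is an understated early response whose size depends partly on the visit date.

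**Working it through.** The plan states no figure for this point. Its one calculated design figure, power of at least 78% in Protocol 9.2, concerns Week 12 and plays no part here. For completeness, a two-sample t-test at 1 SD and two-sided 5% gives 78.1% (16 and 16 patients) and 79.4% (16 and 17), so that figure is reproduced.

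**Inputs.** Baseline and first application on Day 0; Week 1 visit on Day v = 6, 7 or 8; entries from Day v-7 to Day v-1; Baseline mean from Days -7 to -1. Days are counted from Baseline, as in the protocol schedule.

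**Step 1: entries used.** The share is the number of entries dated Day 0 or earlier divided by the number averaged.

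| Visit day | Calendar days used | Before Day 0 | On Day 0 | Share by calendar date | Share, Week 1 diary only | Shared with Baseline |
|---|---|---|---|---|---|---|
| 6 | -1 to 5 | 1 | 1 | 2/7 = 28.6% | 1/6 = 16.7% | Day -1, by calendar date only |
| 7 | 0 to 6 | 0 | 1 | 1/7 = 14.3% | 1/7 = 14.3% | none |
| 8 | 1 to 7 | 0 | 0 | 0 | 0 | none |

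**Step 2: dilution.** Assume a constant effect from Day 1 and none on entries dated Day 0 or earlier. The fraction recovered is 1 minus the share. A true 3.0-point drop then reads as:

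- Day 7: 3.0 × 6/7 = 2.57
- Day 6, by calendar date: 3.0 × 5/7 = 2.14
- Day 6, Week 1 diary only: 3.0 × 5/6 = 2.50
- Day 8: 3.0

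To reach the 3-point flag at Week 1, the true drop would have to be 3/(6/7) = 3.5 points for a Day 7 visit, or 3/(5/7) = 4.2 points for a Day 6 visit by calendar date.

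**Step 3: a gradual effect.** Assume instead a linear rise to 3 points over 28 days, that is 3d/28 on Day d.

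- Day 7: the mean of Days 0 to 6 is 3/28 × 21/7 = 0.32, and of Days 1 to 6 it is 3/28 × 3.5 = 0.38. The difference is about 0.05 points.
- Day 6, by calendar date: the mean is 3/28 × 15/7 = 0.23, against 3/28 × 3 = 0.32 for Days 1 to 5. The difference is about 0.09 points.

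The relative shares are as in Step 1, but the absolute change on a 0 to 10 scale is very small.

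**Step 4: later visits.** The earliest on-schedule visits at Weeks 4, 8 and 12 fall on Days 24, 52 and 80. Their first diary days are 17, 45 and 73, so none reaches Day 0.

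**Step 5: cases beyond Step 1.** The shares assume complete diaries. Protocol 5.1 sets a minimum of four entries for Baseline only. With four entries, one or two early ones would be 1/4 = 25% or 2/4 = 50%. The Week 1 window in SAP 4.6.2 runs over study days 1 to 17, so an off-schedule visit on Day 5, 4 or 3 would by calendar date contain 3/7, 4/7 or 5/7 such entries.

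**The case against.** The strongest reply is that this is small and partly hypothetical.

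- **The Day 0 entry may follow the first application.** It is made at home in a diary received at the Baseline visit. A patient who scores in the morning may make no Day 0 entry in it at all. This stands: treating Day 0 as untreated is an assumption that gives an upper figure. The 24-hour recall still reaches back past the first application, so the entry is not a clean on-treatment score.
- **The Day -1 entry lies in a different diary, already returned.** If the mean is built from the Week 1 diary alone, a Day 6 visit averages six entries and shares none. This stands too. The documents do not say which derivation applies, and that is the gap.
- **The 3-point example needs a full effect at once.** Correct; Step 3 shows how little a gradual effect would be altered.
- **Week 1 is exploratory.** The efficacy endpoints run from Baseline to Week 12, and the logistic models are at Week 12. The in-clinic scores at Week 1 give a second early measure whose 24-hour recall is wholly on treatment on Days 6 to 8. The rule is the same in both arms and pulls toward no effect. All of this stands and limits the importance of the point.

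A reader might infer that every Week 1 mean holds one or two pre-treatment entries. The documents do not support that: a Day 8 visit has none, and a Day 7 visit has no entry dated before the day treatment starts. Nor do they support reading 29%, or a value shared with Baseline, as typical. On schedule, both need a Day 6 visit and a derivation that reuses the Baseline diary.

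**Conclusion.** The point holds as a minor defect in the derivation. Read literally, the rule puts one largely or partly untreated entry into the Week 1 mean for a Day 7 visit (up to about 14% dilution). For a Day 6 visit it puts in one or two (about 17% or 29%, depending on an unstated choice between diaries). For a Day 8 visit it puts in none. These sizes assume complete diaries, a constant effect from Day 1 and a Day 0 entry that reflects untreated time.

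The consequence is confined to the Week 1 itch and pain results. A reader might infer that the primary result is biased through the repeated-measures model or the imputation. The plan does not support that. The model has a treatment-by-visit interaction and the Week 12 diary window is far from Baseline. Week 1 therefore reaches the Week 12 contrast only indirectly, through within-patient correlation and shared covariate coefficients, and mainly for patients with missing later visits. That effect was reasoned from the model's structure, not simulated.

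**What to change.** Add one sentence to SAP 2.4.1: post-baseline weekly means of WI-NRS and WP-NRS use only diary entries dated at least one day after the first application, and never an entry that contributes to the Baseline mean. Record it in SAP 5.6 as a clarification of the protocol's seven-day definition, and settle it before unblinding.

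On-schedule Week 1 means would then rest on 5, 6 or 7 entries for visits on Day 6, 7 or 8. On-schedule means at Weeks 4, 8 and 12 do not change. The work is a date filter in the derivation; no new data are needed.

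There are two costs. Week 1 means rest on slightly fewer entries, and a very early off-schedule visit could leave few or none. The filter is also not perfect: a Day 1 entry made early in the day may still recall some hours before the first application.
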